12.1 Dosing Compliance

Dosing compliance (% compliance) will be assessed by calculating the number of actual doses received and comparing that to the number of expected doses as follows:

$$\text{Compliance (\%)} = \frac{\text{Number of Actual Doses Received}}{\text{Number of Expected Doses}} \times 100\%$$

The number of actual doses received will be calculated from the number of used vials recorded in the CRF after Visit 2 (Day 1). The number of expected doses that will be used for calculating compliance will be calculated as $2x[(\text{date of completion/discontinuation} - \text{date of Visit 2 [Day 1]}) + 1]$ for all subjects with BID dosing. For subjects with TID dosing, the number of expected doses will be calculated as $3x[(\text{date of completion/discontinuation} - \text{date of Visit 2 [Day 1]}) + 1]$.

A categorical dosing compliance variable will also be derived as non-compliant (<80% or >125%) and compliant ($\geq 80\%$ and $\leq 125\%$).

Dosing compliance (%) will be summarized with continuous descriptive statistics for each treatment group, using the mITT and mITT2 populations. The compliance category defined above will be summarized with discrete summary statistics.

A subject listing of dosing compliance will also be produced.

12.2 Treatment Exposure

Extent of treatment exposure for all subjects will be calculated in days using the following:

$$\text{Extent of Exposure (days)} = (\text{Date of completion/discontinuation} - \text{date of Visit 2 [Day 1]}) + 1$$

Extent of treatment exposure (days) for each subject exposed to study drug will be summarized with continuous descriptive statistics for each treatment group, using the Safety population. A subject listing of treatment exposure will also be produced.

13. Efficacy Analyses

13.1 Primary Analysis

The primary efficacy variables (Pre-CAE[®]) are:

- Change from Baseline to Visit 5 (Day 85 ± 2) in inferior corneal staining score (Ora Calibra[®] scale) in the study eye
- Change from Baseline to Visit 5 (Day 85 ± 2) in total corneal staining score (Ora Calibra[®] scale) in the study eye
- Change from Baseline to Visit 5 (Day 85 ± 2) in total corneal staining score (Oxford scale) in the study eye
- Change from Baseline to Visit 5 (Day 85 ± 2) in eye dryness measured using VAS, and
- Change from Baseline to Visit 5 (Day 85 ± 2) in Total OSDI score

For each endpoint, change from baseline will be calculated as visit minus baseline such that a positive difference indicates a worsening of dry eye signs or symptoms. In addition, treatment comparisons between active and vehicle will be calculated as active minus vehicle, such that a negative result indicates a better score for the active treatment (i.e., the active treatment had a smaller increase in dry eye signs or symptoms than the placebo group). For comparisons between active and vehicle, dosing (TID or BID) of the vehicle will match the dosing of the active treatment.

13.1.1 PRE-CAE[®] INFERIOR FLUORESCEIN STAINING (ORA CALIBRA[®] SCALE)

Pre-CAE[®] fluorescein staining in the inferior region of the cornea will be graded using the Ora Calibra[®] Corneal and Conjunctival Staining Scale. The Ora Calibra[®] Corneal and Conjunctival Staining Scale ranges from 0 to 4 (half grade increments may be used), where grade 0 = none, 1 = trace, 2 = mild, 3 = moderate, and 4 = severe.

Changes from baseline in the pre-CAE[®] inferior fluorescein staining scores will be summarized at Visit 5 (Day 85 ± 2) by treatment group for the study eye using quantitative summary statistics. Changes from baseline will be compared between each AXR-159 Ophthalmic Solution group versus vehicle group at matched dosing frequency (TID or BID) using an ANCOVA model that adjusts for baseline. Specifically, the ANCOVA model will include terms for baseline inferior corneal staining score (ICCS) and baseline eye dryness score as covariates and treatment group as a factor in the model. The differences in means, two-sided 95% CIs for the difference in means and p-values will be reported. Pairwise t-tests from the ANCOVA model will be used to compare treatment and vehicle groups.

The following SAS code will be used to run the ANCOVA analysis for each of Stage 1 and Stage 2:

```
PROC MIXED DATA = INDATA;
```

```

CLASS TREATMENT;
MODEL CHANGE_ICSS = BASELINE_ICSS BASELINE_EDS TREATMENT
   / SOLUTION COVB;
LSMEANS TREATMENT / CL PDIFF;
ODS OUTPUT LSMEANS = OUTLS DIFFS = OUTDIFFS;
RUN;

```

where

- *TREATMENT* is the name of the treatment group variable
- *BASELINE_ICSS* is the baseline pre-CAE® inferior fluorescein staining score in the study eye
- *BASELINE_EDS* is the baseline pre-CAE® eye dryness score
- *CHANGE_ICSS* is the pre-CAE® inferior fluorescein staining in the study eye at Visit 5 (Day 85 ± 2) – *BASELINE_ICSS*
- *OUTLS* is the name of the output dataset that contains the statistical results for the treatment means from the ANCOVA model
- *OUTDIFFS* is the name of the output dataset that contains the statistical results for the differences in treatment means from the ANCOVA model

T-tests and Wilcoxon rank sum tests will also be conducted as sensitivity analyses to assess robustness of the results.

The primary analysis will be performed on the mITT population with the LOCF imputation method for missing values. For the LOCF analysis, the last value from the previous visits will be carried forward. Only pre-CAE® or non-CAE® time points will be used to impute a missing pre-CAE® value.

As sensitivity analyses, the primary analysis will also be performed on the mITT2 population with LOCF, the PP population with LOCF, the mITT population with observed data only, and the mITT population with MCMC imputation.

The MCMC method will be performed using the SAS procedure PROC MI. The SAS code for obtaining multiple imputation data is:

```

PROC MI DATA = INDATA SEED = SEED_VALUE OUT = OUTDATA NIMPUTE = 20
   MINIMUM = 0 MAXIMUM = 4 ROUND = 0.5;
   BY TREATMENT
   MCMC INITIAL = EM;
   VAR BASELINE_ICSS ICSS;
RUN;

```

where

- *INDATA* is the name of the input dataset
- *OUTDATA* is the name of the output dataset

- *TREATMENT* is the name of the treatment group variable
- *BASELINE_ICSS* is the baseline pre-CAE® inferior fluorescein staining score in the study eye
- *ICSS* is the pre-CAE® inferior fluorescein staining in the study eye at Visit 5 (Day 85 ± 2)

In the above, the random number seed *SEED_VALUE* will be set to 62521 + S, where S = 1 for Stage 1 data analysis, S = 2 for Stage 2 data analysis, and S = 3 for analysis of the combined Stage 1 and Stage 2 data.

After obtaining twenty complete data sets and calculating changes from baseline, the following SAS code will be used to run the ANCOVA model on each data set and combine the results from the twenty analyses:

```

PROC MIXED DATA = OUTDATA;
  BY _IMPUTATION_;
  CLASS TREATMENT;
  MODEL CHANGE_ICSS = BASELINE_ICSS BASELINE_EDS TREATMENT
    / SOLUTION COVB;
  LSMEANS TREATMENT / CL PDIFF;
  ODS OUTPUT LSMEANS = OUTLS DIFFS = OUTDIFFS;
RUN;
PROC SORT DATA=OUTLS; BY TREATMENT _IMPUTATION_; RUN;
PROC MIANALYZE DATA=OUTLS;
  BY TREATMENT;
  MODELEFFECTS ESTIMATE;
  STDERR STDERR;
RUN;

DATA OUTDIFFS;
  SET OUTDIFFS;
  COMPARISON = TREATMENT||' - '||LEFT(_TREATMENT);
RUN;
PROC SORT DATA=OUTDIFFS; BY COMPARISON _IMPUTATION_; RUN;
PROC MIANALYZE DATA=OUTDIFFS;
  BY COMPARISON;
  MODELEFFECTS ESTIMATE;
  STDERR STDERR;
RUN;

```

where

- *TREATMENT* is the name of the treatment group variable
- *BASELINE_ICSS* is the baseline pre-CAE® inferior fluorescein staining score in the study eye
- *BASELINE_EDS* is the baseline pre-CAE® eye dryness score
- *CHANGE_ICSS* is the pre-CAE® inferior fluorescein staining in the study eye at Visit 5 (Day 85 ± 2) – *BASELINE_ICSS*

- OUTLS is the name of the output dataset that contains the statistical results for the treatment means from the ANCOVA model that is run on each of the twenty imputation datasets
- OUTDIFFS is the name of the output dataset that contains the statistical results for the differences in treatment means from the ANCOVA model that is run on each of the twenty imputation datasets

Similar SAS code will be used to conduct MCMC multiple imputation analysis for t-tests using the same imputation data sets generated above.

Pre-CAE® inferior fluorescein staining changes from baseline in the study eye will be displayed graphically in a bar chart with standard error bars by visit and treatment group based on the ANCOVA analysis.

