8.4 Data Analysis Conventions

All data analysis will be performed by Statistics & Data Corporation (SDC) after the study is completed and the database has been locked and released for unmasking. Statistical programming and analyses will be performed using SAS® Version 9.4 or higher. Output will be provided in rich text format (RTF) for tables and portable document format (PDF) for tables, listings, and figures using landscape orientation. All study data will be listed by subject, treatment, and visit (as applicable) based on all randomized subjects unless otherwise specified.

Summaries for continuous and ordinal variables will include the number of observations (n), arithmetic mean, standard deviation (SD), median, minimum, and maximum). Minima and maxima will be reported with the same precision as the raw values; means and medians will be presented to one additional decimal place than reported in the raw values. SDs will be presented to two additional decimal places than reported in the raw values. Summaries for discrete variables will include frequency counts and percentages. All percentages will be rounded to one decimal place (i.e., XX.X%). Differences between active treatment groups and vehicle will be calculated as Active minus Vehicle and change from baseline will be calculated as follow-up visit minus baseline. The baseline measure will be defined as the last non-missing measure prior to initiation of investigational treatment.

Statistical comparisons between each AXR-159 Ophthalmic Solution group will be to the vehicle group at matched dosing frequency (TID or BID). AXR-159 Ophthalmic Solution plus Artificial Tear group will be compared to both AXR-159 Ophthalmic Solution and to the vehicle group at matched dosing frequency.

A final database lock will occur at the completion of Stage 2 and the safety, tolerability, and efficacy data from both Stage 1 and 2 will be analyzed separately and in a combined fashion to fully leverage the advantage of this two-stage study design.

All statistical tests will be two-sided with a significance level of 0.05 ($\alpha = 0.05$) unless otherwise specified. Confidence intervals (CI) for differences between treatment groups will be two-sided at 95% confidence. All p-values will be rounded to four decimal places; p-values less than 0.0001 will be presented as “<0.0001”; p-values greater than 0.9999 will be presented as “>0.9999”.

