TABLE 14.1.2.3.2	DEMOGRAPHICS – COMBINED STAGE 1 AND STAGE 2	MITT2 POPULATION
TABLE 14.1.2.3.3	DEMOGRAPHICS – COMBINED STAGE 1 AND STAGE 2	SAFETY POPULATION
TABLE 14.1.3.1.1	OCULAR MEDICAL HISTORY – STAGE 1	MITT POPULATION
TABLE 14.1.3.1.2	OCULAR MEDICAL HISTORY – STAGE 2	MITT POPULATION
TABLE 14.1.3.1.3	OCULAR MEDICAL HISTORY – COMBINED STAGE 1 AND STAGE 2	MITT POPULATION
TABLE 14.1.3.2.1	NON-OCULAR MEDICAL HISTORY – STAGE 1	MITT POPULATION
TABLE 14.1.3.2.2	NON-OCULAR MEDICAL HISTORY – STAGE 2	MITT POPULATION
TABLE 14.1.3.2.3	NON-OCULAR MEDICAL HISTORY – COMBINED STAGE 1 AND STAGE 2	MITT POPULATION

Table Number	Title	Population
TABLE 14.1.4.1.1	CONCOMITANT OCULAR MEDICATIONS BY TREATMENT GROUP, DRUG CLASS AND PREFERRED NAME – STAGE 1	MITT POPULATION
TABLE 14.1.4.1.2	CONCOMITANT OCULAR MEDICATIONS BY TREATMENT GROUP, DRUG CLASS AND PREFERRED NAME – STAGE 2	MITT POPULATION
TABLE 14.1.4.1.3	CONCOMITANT OCULAR MEDICATIONS BY TREATMENT GROUP, DRUG CLASS AND PREFERRED NAME – COMBINED STAGE 1 AND STAGE 2	MITT POPULATION
TABLE 14.1.4.2.1	CONCOMITANT NON-OCULAR MEDICATIONS BY TREATMENT GROUP, DRUG CLASS AND PREFERRED NAME – STAGE 1	MITT POPULATION
TABLE 14.1.4.2.2	CONCOMITANT NON-OCULAR MEDICATIONS BY TREATMENT GROUP, DRUG CLASS AND PREFERRED NAME – STAGE 2	MITT POPULATION
TABLE 14.1.4.2.3	CONCOMITANT NON-OCULAR MEDICATIONS BY TREATMENT GROUP, DRUG CLASS AND PREFERRED NAME – COMBINED STAGE 1 AND STAGE 2	MITT POPULATION
TABLE 14.2.1.1.1	PRE-CAE® INFERIOR CORNEAL FLUORESCEIN STAINING (ORA CALIBRA® SCALE) – STAGE 1	MITT POPULATION WITH LOCF
TABLE 14.2.1.1.2	PRE-CAE® INFERIOR CORNEAL FLUORESCEIN STAINING (ORA CALIBRA® SCALE) – STAGE 2	MITT POPULATION WITH LOCF
TABLE 14.2.1.1.3	PRE-CAE® INFERIOR CORNEAL FLUORESCEIN STAINING (ORA CALIBRA® SCALE) – COMBINED STAGE 1 AND STAGE 2	MITT POPULATION WITH LOCF
TABLE 14.2.1.2.1	PRE-CAE® INFERIOR CORNEAL FLUORESCEIN STAINING (ORA CALIBRA® SCALE) – STAGE 1	MITT2 POPULATION WITH LOCF
TABLE 14.2.1.2.2	PRE-CAE® INFERIOR CORNEAL FLUORESCEIN STAINING (ORA CALIBRA® SCALE) – STAGE 2	MITT2 POPULATION WITH LOCF
TABLE 14.2.1.2.3	PRE-CAE® INFERIOR CORNEAL FLUORESCEIN STAINING (ORA CALIBRA® SCALE) – COMBINED STAGE 1 AND STAGE 2	MITT2 POPULATION WITH LOCF
TABLE 14.2.1.3.1	PRE-CAE® INFERIOR CORNEAL FLUORESCEIN STAINING (ORA CALIBRA® SCALE) – STAGE 1	PP POPULATION WITH LOCF
TABLE 14.2.1.3.2	PRE-CAE® INFERIOR CORNEAL FLUORESCEIN STAINING (ORA CALIBRA® SCALE) – STAGE 2	PP POPULATION WITH LOCF

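### The combined Stage 1 + Stage 2 ANCOVAs of the primary endpoints specify no stage term, although the combined CMH tests are stratified by stage

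*SAP*

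**What the plan says.** SAP section 8.4 states that "efficacy data from both Stage 1 and 2 will be analyzed separately and in a combined fashion". The table list in SAP section 20 accordingly has a combined version of each primary table. One example is Table 14.2.1.1.3, "PRE-CAE® INFERIOR CORNEAL FLUORESCEIN STAINING (ORA CALIBRA® SCALE) – COMBINED STAGE 1 AND STAGE 2", in the mITT population with LOCF.

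The model in SAP 13.1.1 is described as follows: "the ANCOVA model will include terms for baseline inferior corneal staining score (ICCS) and baseline eye dryness score as covariates and treatment group". SAP 13.1.2 to 13.1.5 give the same kind of list for the other four primary endpoints, with the endpoint's own baseline. Protocol 12.4.5 agrees. Neither stage nor site is a term anywhere.

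Two pieces of code bear on the combined data:

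- The LOCF code is introduced with "The following SAS code will be used to run the ANCOVA analysis for each of Stage 1 and Stage 2". No combined LOCF model is written.
- The multiple-imputation code does cover the combined data, because its seed rule includes "S = 3 for analysis of the combined Stage 1 and Stage 2 data". Its `MODEL` statement has no stage. Its imputation step runs by treatment only, with "VAR BASELINE_ICSS ICSS" as the variables.

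By contrast, every CMH analysis of the combined data (SAP 13.2.1, for example) adds stage as a stratification factor.

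**The concern.** Stage is not balanced across arms by design. Stage 1 allocates 4:1 in the lead-in cohorts and 1:1 in the expansion. Stage 2 allocates up to 2:2:2:2:1:1:1, so an active arm is twice the size of its matched vehicle. Some Stage 2 arms have no Stage 1 patients at all. Stage 1 runs at up to 2 sites and Stage 2 at up to 7 (Protocol 7.1). A difference between stages in sites, graders, season or vehicle response is therefore possible, and the baseline covariates would not remove it. A model without stage attributes part of any such difference to treatment.

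The SAP also leaves open whether Stage 1 vehicle patients serve, in the combined analysis, as controls for arms that exist only in Stage 2. Sections 5 and 8.4 allow that reading: section 5 counts a combined matching vehicle group, and section 8.4 defines comparisons by dosing frequency and not by stage. Neither section states it.

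The final analysis declares significance at two-sided p < 0.05 (Protocol 12.4.8). An unmodelled shift could produce a false positive or hide a real effect, depending on its sign. If the model is left unspecified, it may be chosen after unmasking.

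**Working it through.** **Plan's own figure.** With 93 active and 60 vehicle patients, a difference of 0.35, SD 0.75 and a two-sided t-test at 0.05, the noncentral t gives 80.0% power, as stated. The numbers also follow from 10% loss: 103 × 0.9 = 92.7 and 67 × 0.9 = 60.3. The sample size is not at fault.

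**Inputs.** Stage 1 sizes, active and vehicle, come from Protocol 6.1:

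- 50 mg/mL TID expanded: 8 + 45 = 53 and 2 + 45 = 47.
- 30 mg/mL TID expanded: 8 + 40 = 48 and 2 + 40 = 42.
- 30 mg/mL BID expanded: 8 + 35 = 43 and 2 + 35 = 37.

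Stage 2 has 60 per active arm and 30 matched vehicle (SAP section 5).

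**Bias.** Let D be the Stage 1 minus Stage 2 difference in mean change that the covariates leave unexplained. Without a stage term, the bias in active minus vehicle = (active Stage 1 share − vehicle Stage 1 share) × D.

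| Pathway | Carried arm | Stage-2-only arm, Stage 1 vehicle pooled |
|---|---|---|
| 50 mg/mL TID | 53/113 − 47/77 = 0.469 − 0.610 = −0.14 | 0 − 0.61 |
| 30 mg/mL TID | 48/108 − 42/72 = 0.444 − 0.583 = −0.14 | 0 − 0.58 |
| 30 mg/mL BID | 43/103 − 37/67 = 0.417 − 0.552 = −0.13 | 0 − 0.55 |

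The second column of weights applies to arms at the expanded dosing frequency. A change score above zero is a worsening, so D > 0 (less improvement in Stage 1) favours the drug and D < 0 works against it. Where both compared arms come from Stage 2 only, such as 50 mg/mL BID against BID vehicle on the first pathway, the bias is zero.

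**Type I error.** The documents give no D, so 0.10, 0.25 and 0.35 are assumptions. The last two equal the reference drug's effect and the target effect, and are upper cases. Evaluable numbers after 10% loss are 48/42, 43/38 and 39/33 in Stage 1, and 54 and 27 in Stage 2. Results are from 200,000 simulated null trials per setting with residual SD 0.75.

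| Pathway | Carried arm | Stage-2-only arm at D = 0.10, 0.25, 0.35 |
|---|---|---|
| 50 mg/mL TID | 0.05–0.07 | 0.07, 0.20, 0.33 |
| 30 mg/mL TID | 0.05–0.07 | 0.07, 0.18, 0.30 |
| 30 mg/mL BID | 0.05–0.07 | 0.07, 0.16, 0.26 |

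A closed-form check with the SD held at 0.75 agrees within about 0.02. With stage in the model, type I error is 0.049 to 0.051 throughout, provided the stage effect is additive.

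**Opposite sign.** On the 50 mg/mL TID pathway with D = −0.10, −0.25 and −0.35, power for 0.35 units falls from 73% to 56%, 30% and 17% for a Stage-2-only TID arm. For the carried arm it falls from 85% to 82%, 77% and 72%.

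**Alternative 1:1:1:1 Stage 2 (60 vehicle).** The carried-arm weight is 53/113 − 47/107 = 0.469 − 0.439 = 0.03, with type I error 0.05. The Stage-2-only weight is 47/107 = 0.44 in size, with type I error 0.06, 0.13 and 0.21.

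**Standard errors, 50 mg/mL TID pathway.**

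- Carried arm without stage: 0.75 × √(1/102 + 1/69) = 0.117. With stage, the information is 48×42/90 + 54×27/81 = 22.4 + 18 = 40.4, so the SE is 0.75/√40.4 = 0.118.
- Stage-2-only arm without stage: 0.75 × √(1/54 + 1/69) = 0.136. With stage, least squares on the planned layout gives 0.153.
- Stage 2 data alone: 0.75 × √(1/54 + 1/27) = 0.177.

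**The case against.** The strongest reply is that little harm is shown where it counts. The comparison that the sample size describes is the carried arm, which takes up only 13–14% of a shift, or 3% under 1:1:1:1. Efficacy is declared exploratory and is unadjusted for several arms and endpoints (SAP 8.5), so a type I error of 0.07 at most is a minor addition. That stands.

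The large figures need two things that the documents do not state: pooling of Stage 1 vehicle, and a residual shift of 0.25 to 0.35. Eligibility, run-in and enrolment targets are common to both stages, and baseline staining and eye dryness are covariates. This also stands. The size is conditional, although the covariates cannot remove a shift due to sites or graders.

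Separate Stage 2 analyses already give Stage-2-only arms concurrent controls. Table 14.2.1.1.2, "PRE-CAE® INFERIOR CORNEAL FLUORESCEIN STAINING (ORA CALIBRA® SCALE) – STAGE 2", is one. That is correct and limits the damage, but the combined tables will still be produced.

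The printed LOCF code is for the separate stages, so for LOCF the exact statement is that no combined model with stage is specified. Only the multiple-imputation code is tied to the combined data, and that is a sensitivity analysis.

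The BID pathway rests on an inferred 30 mg/mL BID arm of 60 in Stage 2 (43 + 60 = 103 in SAP section 5), which SAP 3.1 does not list, so its row carries less weight. The magnitudes are worked out for inferior staining only.

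Finally, adding stage lowers nominal power for Stage-2-only arms. The power given up, however, is valid only when D = 0. None of these points supplies a reason to adjust the binary secondary endpoints for stage and not the primary ones.

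**Conclusion.** The concern holds and should be fixed. The omission is a matter of text, and the share weights follow from the planned arm sizes; both are firm. For the carried arm the consequence is small: a bias of 0.13–0.14 × D and type I error of at most 0.07. For Stage-2-only arms at the expanded frequency it is 0.55–0.61 × D, and type I error can reach 0.26–0.33 at the largest assumed shift. That larger figure depends on Stage 1 vehicle being pooled and on an assumed D. The direction follows the sign of the shift. Separate-stage analyses are unaffected. This is a specification gap in an exploratory trial, not a fatal flaw.

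**What to change.** 1. In SAP 13.1.1 to 13.1.5, write the combined-stage model with `STAGE` in `CLASS` and `MODEL` for the LOCF, observed-data and multiple-imputation versions. Use the same term in the combined secondary ANCOVAs (SAP 13.2).
2. Account for stage in the combined-data imputation. Impute by treatment and stage, or put stage in the imputation model where a cell is small; a halted Stage 1 cohort has only 8 active and 2 vehicle patients.
3. State which vehicle patients are the control for Stage-2-only arms in the combined analysis, and name the planned separate Stage 2 ANCOVA as their concurrent-control comparison.
4. SAP 13.1.1 says "T-tests and Wilcoxon rank sum tests will also be conducted as sensitivity analyses to assess robustness of the results". Note that on combined data these unstratified tests have the same limitation.

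The cost is SAP wording and one model term, with no added patients or analyses. Power for 0.35 units, without and then with stage:

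| Pathway | Carried arm | Stage-2-only arm |
|---|---|---|
| 50 mg/mL TID | 85% to 84% | 73% to 62% |
| 30 mg/mL TID | 83% to 82% | 72% to 62% |
| 30 mg/mL BID | 80% to 79% | 70% to 61% |

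Before rounding, each carried-arm loss is under one point. The planned Stage 2 ANCOVA alone (SE 0.177) has about 50% power for the Stage-2-only arms.

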10.1.4 Procedures for Final Study Entry

Subjects must meet all inclusion and none of the exclusion criteria.

10.1.5 Methods for Assignment to Treatment Groups:

Prior to initiation of study run-in (at Visit 1), each subject who qualifies for entry will be assigned a screening number. All screening numbers will be assigned in strict numerical sequence at a site and no numbers will be skipped or omitted. If all inclusion and exclusion criteria are met at Visits 1 and 2, each qualifying subject will then be assigned a randomization number at the end of Visit 2.

A randomization schedule will be provided to each investigational site. The randomization schedule will use block randomization stratified by site, such that there will be an approximate equal number of subjects assigned to each of the two treatment arms at each site for the Stage 1, Expansion Cohort. For Stage 1, Cohorts 1-3 patients with signs and symptoms of DED will be randomly assigned in a 4:1 ratio to receive either a single concentration of AXR-159 Ophthalmic Solution or AXR-159 Ophthalmic Solution Vehicle. The site staff will dispense to the patient the study kit labelled with the corresponding randomization number. The randomization number will be recorded on the patient's source document and eCRF. New kits will be dispensed at Visits 2, 3, and 4 based on the subject's randomization. The Sponsor, Investigators, and study staff will be masked during the randomization process and throughout the study.

During the run-in period, the patients will all be supplied with AXR-159 Ophthalmic Solution Vehicle. Patients will be informed that they will receive only vehicle during the 2-week run-in period. Following the run-in period the patient, site personnel, the sponsor and patients will be masked to the treatment assignment for the 3 month treatment period. All study medication will be provided in identical unit of dose vials and cartons to maintain masking of the study.

For both Stages 1 and 2, patients with signs and symptoms of DED will be randomly assigned in a 4:1 (Stage 1, Cohorts 1-3) ratio, a 1:1 (Stage 1, Expansion Cohort) ratio, or to a 2:2:2:2:1:1:1 (Stage 2) ratio to receive either a single concentration of AXR-159 Ophthalmic Solution or AXR-159 Ophthalmic Solution Vehicle.

For the expansion cohort in Stage 1 and Stage 2, subjects will be randomized by strata as follows:

- Site
- Baseline eye dryness score ≥ 60 , < 60
- Baseline inferior corneal staining > 1.5 , ≤ 1.5

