Subjects will not be stratified in Cohorts 1, 2 and 3 in Stage 1.

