12.4.5 Primary Efficacy Analyses

The primary efficacy variables (Pre-CAE®) are:

- Change from Baseline to Month 3 in inferior corneal staining score (Ora Calibra® scale) in the study eye
- Change from Baseline to Month 3 in total corneal staining score (Oxford and Ora Calibra® scales) in the study eye
- Change from Baseline to Month 3 in eye dryness measured using a visual analogue scale (VAS)
- Change from Baseline to Month 3 in Total Ocular Surface Disease Index (OSDI) score, and

The primary variables will be summarized as described in [Section 12.4.1](#). The primary efficacy analysis will use the mITT population with LOCF.

Statistical tests will be performed for each AXR-159 Ophthalmic Solution group versus vehicle group at matched dosing frequency (TID or BID). ANCOVA models will be used to compare the change from baseline primary efficacy variables. The ANCOVA models will include terms for baseline value, baseline inferior corneal staining score (ICCS) and baseline eye dryness score as covariates and treatment (AXR-159 or vehicle) as a factor in the model. Pairwise comparisons will be performed for each AXR-159 treatment group versus vehicle using t-tests of the least square means from this model. Two-sided confidence intervals (95%) will be provided for the differences between treatments. As supportive analyses, two-sample t-tests and Wilcoxon rank sum tests will also be conducted.

Details of additional supportive primary efficacy analyses will be provided in the statistical analysis plan.

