12.4.6 Secondary Efficacy Analyses

Continuous secondary efficacy variables (see [Section 8.1.2](#)) and changes from baseline in these measures will be summarized as described in [Section 12.4.1](#), and analyzed by visit using ANCOVA as described for the primary efficacy analyses.

Binary clinical cure variables representing clinical cure will be defined by visit for TBUT ≥ 10 , Schirmer's test ≥ 10 mm, Total OSDI < 18 , and Ocular Discomfort Score = 0. These binary variables will be summarized as described in [Section 12.4.1](#). Additionally, within each treatment group, shift tables for complete treatment response (yes/no) in the study eye relative to baseline will be presented for each variable.

The Cochran-Mantel-Haenszel test, stratified by baseline inferior corneal staining score (ICCS, > 1.5 and ≤ 1.5) and eye dryness score (≥ 60 and < 60) will be used to compare treatments with respect to the proportion of cured patients. Pairwise comparisons will be performed for each AXR-159 treatment group versus vehicle. Two-sided confidence intervals (95%) will be provided for the differences between treatments. The confidence intervals will be constructed using the normal approximation to the binomial distribution.

The secondary efficacy analysis will use the mITT population with observed data only.

Details of additional secondary efficacy analyses will be provided in the statistical analysis plan.

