4.1 Method of Assigning Subjects to Treatment Groups

Prior to initiation of study run-in (at Visit 1), each subject who qualifies for entry will be assigned a screening number. All screening numbers will be assigned in strict numerical sequence at a site and no numbers will be skipped or omitted. If all inclusion and exclusion criteria are met at Visits 1 and 2, each qualifying subject will then be assigned a randomization number at the end of Visit 2.

A randomization schedule will be provided to each investigational site. The randomization schedule will use block randomization stratified by site, such that there will be an approximate equal number of subjects assigned to each of the two treatment arms at each site for the Stage 1, Expansion Cohort. For Stage 1, Cohorts 1-3 patients with signs and symptoms of DED will be randomly assigned in a 4:1 ratio to receive either a single concentration of AXR-159 Ophthalmic Solution or AXR-159 Ophthalmic Solution Vehicle. The site staff will dispense to the patient the study kit labelled with the corresponding randomization number. The randomization number will be recorded on the patient's source document and eCRF. New kits will be dispensed at Visits 2, 3, and 4 based on the subject's randomization. The Sponsor, Investigators, and study staff will be masked during the randomization process and throughout the study.

During the run-in period, the patients will all be supplied with AXR-159 Ophthalmic Solution Vehicle. Patients will be informed that they will receive only vehicle during the 2-week run-in period. Following the run-in period the patient, site personnel, the sponsor and patients will be masked to the treatment

assignment for the 3 month treatment period. All study medication will be provided in identical unit of dose vials and cartons to maintain masking of the study.

For both Stages 1 and 2, patients with signs and symptoms of DED will be randomly assigned in a 4:1 (Stage 1, Cohorts 1-3) ratio, a 1:1 (Stage 1, Expansion Cohort) ratio, or to a 2:2:2:2:1:1:1 (Stage 2) ratio to receive either a single concentration of AXR-159 Ophthalmic Solution or AXR-159 Ophthalmic Solution Vehicle. For the expansion cohort in Stage 1 and Stage 2, subjects will be randomized by strata as follows:

- Site
- Baseline eye dryness score ≥ 60 , < 60
- Baseline inferior corneal staining > 1.5 , ≤ 1.5

Subjects will not be stratified in Cohorts 1, 2 and 3 in Stage 1.

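### Site is a randomisation stratum but no ANCOVA adjusts for it, and no combined-stage ANCOVA has a stage term: a small, conditional loss that is cheap to remove

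*SAP*

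**What the plan says.** **Randomisation.** Protocol 10.1.5 states: "The randomization schedule will use block randomization stratified by site". SAP 4.1 adds: "For the expansion cohort in Stage 1 and Stage 2, subjects will be randomized by strata as follows", and lists site, eye dryness (cut at 60) and inferior corneal staining (cut at 1.5). The dose-finding cohorts are the exception: "Subjects will not be stratified in Cohorts 1, 2 and 3 in Stage 1".

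**Primary model.** Protocol 12.4.5: "The ANCOVA models will include terms for baseline value, baseline inferior corneal staining score (ICCS) and baseline eye dryness score as covariates", with treatment as the factor. SAP 13.1.1 specifies that "the ANCOVA model will include terms for baseline inferior corneal staining score (ICCS) and baseline eye dryness score as covariates and treatment group", and its code has the same content: "MODEL CHANGE_ICSS = BASELINE_ICSS BASELINE_EDS TREATMENT". SAP 13.1.2 to 13.1.5 repeat it for the other primary variables, adding each one's own baseline where it differs. The multiple-imputation code uses the same model, and the secondary ANCOVAs in SAP 13.2 use the same covariates.

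**Secondary responder tests.** In Protocol 12.4.6 the CMH test is "stratified by baseline inferior corneal staining score (ICCS, > 1.5 and ≤ 1.5) and eye dryness score". SAP 13.2 adds study stage as a CMH stratum when the two stages are combined.

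**Combined data.** SAP 8.4 plans separate and combined analyses, and the table list includes combined-stage primary tables. The ANCOVA code in 13.1.1 is introduced for each stage only. No ANCOVA with a stage term is written out.

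Neither document explains why site is omitted or plans a site-adjusted sensitivity analysis.

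**The concern.** The plan balances the arms on three factors and then adjusts for two. When arms are balanced within sites, differences between sites do not contribute to the true sampling error of the treatment difference. A model without site still counts them in its residual, so the reported standard error is too large and power is lost.

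There is a reason to expect some site differences in the staining scores, which supply three of the five primary variables in SAP 13.1. An examiner grades them at up to 2 sites in Stage 1 and up to 7 in Stage 2. Protocol Appendix 2 asks for the same examiner for intraocular pressure, but states no such rule for staining; the procedures it cites may do so. This reasoning does not reach eye dryness (VAS) or total OSDI, which patients report.

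A second issue arises on pooling. The active-to-vehicle ratio differs between the stages, so a model with neither stage nor site lets any stage difference in mean change leak into the treatment estimate.

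**Working it through.** **1. The plan's own figure.** Inputs from Protocol 12.1 and SAP 5: difference 0.35, SD 0.75, 93 active, 60 vehicle, two-sided 5%.

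- SE = 0.75 × √(1/93 + 1/60) = 0.1242; 0.35/0.1242 = 2.818.
- Power = 80.0% (noncentral t) or 80.5% (normal approximation). The stated 80% reproduces.
- 93 and 60 are the lower combined-stage totals after 10% dropout: (43 + 60) × 0.9 = 92.7 and (37 + 30) × 0.9 = 60.3.

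**2. Omitting site under idealised balance.** Let ρ be the between-site share of the variance of change. It is not in the documents; 5%, 10% and 20% are assumed. With exact balance within sites:

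- reported SE / true SE = 1/√(1 − ρ)
- actual α = 2 × [1 − Φ(1.96/√(1 − ρ))]
- power without site = Φ((2.818 − 1.96)/√(1 − ρ))
- power with site = Φ(2.818/√(1 − ρ) − 1.96)

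| ρ | SE ratio | actual α | power without site | power with site | points lost |
|---|---|---|---|---|---|
| 5% | 1.026 | 4.4% | 81.1% | 82.4% | 1.3 |
| 10% | 1.054 | 3.9% | 81.7% | 84.4% | 2.7 |
| 20% | 1.118 | 2.8% | 83.1% | 88.3% | 5.2 |

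This is an upper bound on the effect, because the planned cells are too small for exact balance. In Stage 2, 330 patients over 7 sites × 4 strata give 330/28 ≈ 12 per cell, while the 2:2:2:2:1:1:1 ratio needs blocks of 11.

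**3. Simulation of the planned design.** There were 15,000 null trials per setting (Monte Carlo SE about 0.2 points).

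- Stage 1: 10 unstratified patients at 8:2, plus 90 in blocks within site and the four dryness-by-staining strata, at 2 sites.
- Stage 2: 330 patients in blocks of 11 at 7 sites, comparing one TID active arm with TID vehicle.
- 10% dropout. The SAP ANCOVA was fitted with and without site.
- Assumed: block sizes of 4 and 11, equal expected site sizes, different sites in the two stages.

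Type I error without site (with site in brackets):

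| ρ | Stage 1 | Stage 2 | Combined |
|---|---|---|---|
| 5% | 4.7% (4.9%) | 4.7% (5.1%) | 5.0% (5.2%) |
| 10% | 4.4% (4.7%) | 4.4% (5.1%) | 5.1% (5.3%) |
| 20% | 4.2% (5.0%) | 3.4% (4.6%) | 4.5% (5.0%) |

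Without site, the ratio of reported to empirical SE is 1.01 to 1.09 within a stage and 0.99 to 1.02 in the combined data. On pooling, the excess in the standard error is offset by extra variation from the uneven stage mix.

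**4. Stage mix in the combined data.** On the path where Cohort 1 expands, the upper figures in Protocol 12.1 apply: Stage 1 gives 53 active and 47 vehicle, and Stage 2 gives 60 active and 30 matched vehicle.

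- Active from Stage 1: 53/113 = 46.9%. Matched vehicle from Stage 1: 47/77 = 61.0%. Difference: −14.1 points.
- Bias of the unadjusted difference = −0.141 × stage difference in mean change. For an assumed 0.2 units this is 0.028 in size, about 8% of the 0.35 target (0.028/0.35). Its sign depends on which stage improves more.
- With 60 vehicle patients in Stage 2, the vehicle share becomes 47/107 = 43.9%, the gap 3.0 points and the bias about 0.006 units. The concern is therefore specific to the matched-vehicle comparison at 2:1.

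**The case against.** **The size rests on an assumption.** No between-site variance is given, and the outcome is a change score with baseline as a covariate. A consistently harsh or lenient grader therefore largely cancels, and only site differences in change matter. This stands, and is why the point is conditional.

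**The error is in the safe direction, in an exploratory trial.** SAP 8.5 calls all efficacy analyses exploratory and makes no multiplicity adjustment. A stage-specific test running at 4.4% instead of 5% would rarely change a Phase 2 decision. This also stands, and it keeps the point minor.

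**A reader might infer that p-values are miscalibrated throughout.** The documents do not support that. The 93 and 60 come from pooling two stages with different sites and ratios, not from one balanced seven-site trial, and the simulated type I error for the pooled analysis is 4.5% to 5.1%. Nothing found here inflates false positives.

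**A reader might also blame the unstratified cohorts or the CMH tests.** Under Protocol 6.1 a later cohort starts only if the previous one is judged unsafe or poorly tolerated. On the main path only 10 of about 100 Stage 1 patients are unstratified, and any site imbalance among them is due to chance. The CMH tests are secondary, and adding site to their strata would make the cells too sparse.

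**Conclusion.** The omission is real and unexplained; its consequence is modest. For site shares of 5% to 20%, the stage-specific tests are mildly conservative: about 4.2% to 4.7% in Stage 1 and 3.4% to 4.7% in Stage 2. The power given up is about 1 to 5 points at 93 versus 60, and that figure needs exact balance within sites. If sites do not differ in change, nothing is lost.

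In the combined analysis, which carries the stated power, the clearer defect is the missing stage term. A bias of about 0.03 units follows if the stages differ by 0.2 units in mean change and the comparison is 113 active versus 77 matched vehicle. The plan already recognises stage in its combined CMH tests, so leaving it unspecified in the ANCOVA is inconsistent.

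This is a minor, cheap improvement, held with moderate confidence because both driving quantities are assumed.

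**What to change.** - **Stage-specific ANCOVAs, primary and secondary:** add SITE to the CLASS and MODEL statements, including the ANCOVA run on the multiply imputed data sets.
- **Combined-stage ANCOVAs:** write the model out, with STAGE and site, or site within stage.
- **Small sites:** fix a pooling rule in the SAP before unmasking.
- **CMH tests:** leave the strata as they are.

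If the sponsor prefers to keep the present model, the SAP should at least say why site is omitted and add a site- and stage-adjusted sensitivity analysis.

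The cost is one or two model terms and a short SAP paragraph. The terms use up to 6 degrees of freedom in Stage 2 (7 sites − 1), and up to 8 in the combined model if the stages share no sites (2 + 7 − 1). No new data are needed. SAP section 18, which reports no changes from the protocol's analyses, would need an entry.
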